13.6 Record Storage and Retention

Records of subjects, source documents, monitoring visit logs, CRFs, inventory of study product, regulatory documents, and other Sponsor correspondence pertaining to the study must be kept in the appropriate study files at the site. Source data is defined as all information in original records and certified copies of original records of clinical findings, observations, or other activities in a clinical study necessary for the evaluation and reconstruction of the clinical study. Source data are contained in source documents (original records or certified copies). These records will be retained in a secure file for the period as set forth in the Clinical Study Agreement. Prior to transfer or destruction of these records, the Sponsor must be notified in writing and be given the opportunity to further store such records.

To enable evaluations and/or audits from regulatory authorities or the Sponsor, the Investigator will keep records, including the identity of all participating subjects (sufficient information to link records, e.g., CRFs and hospital records), all original signed ICFs, copies of all CRFs, SAE forms, source documents, and detailed records of treatment disposition. The records should be retained by the Investigator according to specifications in the ICH guidelines, local regulations, or as specified in the Clinical Study Agreement, whichever is longer. The Investigator must obtain written permission from the Sponsor before disposing of any records, even if retention requirements have been met.

If the Investigator relocates, retires, or for any reason withdraws from the study, the Sponsor should be prospectively notified. The study records must be transferred to an acceptable designee, such as another Investigator, another institution, or to the Sponsor.

13.7 Protocol Amendments and Deviations

Any amendments to the study protocol will be communicated to the Investigator by the Sponsor or authorized representative. All protocol amendments will undergo the same review and approval process as the original protocol. A protocol amendment may be implemented only after it has been approved by the IRB, unless immediate implementation of the change is necessary for subject safety. In this case, the situation must be documented and reported to the Sponsor immediately and to the IRB within 5 working days.

13.8 Access to Source Documentation

The Sponsor (or the Sponsor's authorized representative) must have access to inspect all documents and records that are to be maintained by the Investigator, including, but not limited to, medical records (office, clinic, or hospital) for the subjects in this trial. These regulations also allow the Sponsor's records to be inspected by authorized representatives of the FDA or other regulatory authorities. The names and identities of all research subjects will be kept in strict confidence and will not appear on CRFs or other records that are provided to or retained by the Sponsor (or the Sponsor's authorized representative).

13.9 Financial Disclosure

Clinical Investigators are required to provide financial disclosure information to the Sponsor to permit the Sponsor to fulfill its obligations under 21 CFR §54. In addition, investigators must commit to promptly updating this information if any relevant changes occur during the study and for a period of 1 year after the completion of the study.

For this study, any personnel listed on the FDA 1572 Form will be required to provide financial disclosure information.

13.10 Publication Policy

Manuscript(s) and abstract(s) may only be prepared through cooperation between the Sponsor (or designee) and the study Investigator(s). The Investigator agrees not to publish or publicly present any results of the study without prior written consent of the Sponsor.

16.1 Schedule of Assessments

	Days -28 thru 0	PERIOD 1 Cr							Follow- Up/				
		P1 Day 1	P 1 Wk 1	P1 Wk2	P1 Wk6	P1 Wk 12*		P2 Day 1*	P2 Wk 1	P2 Wk 2	P2 Wk 6	P2 Wk 12 (Early Term ^a)	P2 Wk 1
Target Day within each Period	-28-0	1	7±2	14±2	42±3	84±3		1	7±2	14±2	42±3	84±3	91±2
Clinic Visit	X	X		X	X	X				X	X	X	
Telephone Call			X						X				X
Informed Consent	X		İ İ						3				
Eligibility	X	X b											
Medical /Surgical History	X												
Demographic /Social History	X												
Physical Exam	X												
Abbreviated PE		Xb										X	
Ht, Wt, BMI	X					Xc						X ^c	
Vital Signs ^d	X	X^b		X	X	X		X		X	X	X	
ECGs (single)	X			X		X		X		X		X	
Chemistry and Hematology	X	20		X		X				X		X	
Urinalysis	X					X						X	
Suicidality	X		X	X	X	X			X	X	X	X	
PK and Biomarker Sampling	X					X						X	
Randomization		X											
Dispense Test Medication		X			X			X			X		
1st Dose of Medication		X											
Stanford-Binet	Xe												
NIH-TCB		X			X	X					X	X	
KiTAP		X			X	X					X	X	
CGI-S f		X			X	X					X	X	
CGI-I ^f					X	X					X	X	
VAS		X			X	X					X	X	
ABC		X				X						X	
ADAMS		X				X						X	
Vineland-3 ^f		Xe				X						X	

Protocol: BPN14770-CNS-203 Tetra Discovery Partners, Inc.
Date: 25 June 2018 Confidential

	Days -28 thru 0		I	PERIO	D 1		Cross- over		Follow- Up/				
		P1 Day 1	P 1 Wk 1	P1 Wk2	P1 Wk6	P1 Wk 12*		P2 Day 1*	P2 Wk 1	P2 Wk 2	P2 Wk 6	P2 Wk 12 (Early Term ^a)	Wk 1
Target Day within each Period	-28-0	1	7±2	14±2	42±3	84±3		1	7±2	14±2	42±3	84±3	91±2
Clinic Visit	X	X		X	X	X				X	X	X	
Telephone Call			X						X				X
ERP		X				X						X	
Eye Tracking		X				X						X	
IP accountability				X	X	X			3	X	X	X	
Con Meds	X	X	X	X	X	X			X	X	X	X	X
Adverse Events		X	X	X	X	X		X	X	X	X	X	X
Final Disposition													X

^{*}Note: Period 1 Wk 12 and Period 2 Day 1 visits may be combined

^a If early termination occurs, the Week 12 procedures should be completed at the time of the subject's withdrawal (if possible).

^bDo not need to repeat if screening and baseline done at same visit.

^c Weight only

^d Vital signs include pulse rate, blood pressure, respiration rate, and temperature.

^e If the site has performed a Stanford-Binet test or Vineland-3 assessment on the subject in the 6 months prior to screening, the results of these assessments may be used for this study.

f The CGI-S, CGI-I and Vineland-3 assessments may be conducted over the telephone, if necessary.

Clinical Study Report: BPN14770-CNS-203

Protocol: BPN14770-CNS-203 Tetra Discovery Partners, Inc.
Date: 25 June 2018 Confidential

16.2 Clinical Laboratory Analytes

Standard Chemistry

Alanine aminotransferase (ALT)

Albumin

Alkaline phosphatase Aspartate aminotransferase (AST)
Bicarbonate Blood urea nitrogen (BUN)

Calcium Chloride
Creatinine Glucose
Potassium Sodium
Total bilirubin Total protein

Hematology

Hematocrit Hemoglobin

Platelet count Red blood cell (RBC)

Mean corpuscular hemoglobin concentration (MCHC) Mean corpuscular hemoglobin (MCH) White blood cell count and differential (basophils, Mean corpuscular volume (MCV)

eosinophils, lymphocytes, monocytes, and neutrophils)

Urinalysis

Bilirubin Blood
Glucose Ketones
Nitrite pH

Protein Specific Gravity
Urobilinogen Leukocyte esterase

If protein, urine occult blood, nitrite, or leukocyte esterase values are out of range, the microscopic examination will be reported.

1 LIST OF ABBREVIATIONS AND DEFINITIONS OF TERMS

Abbreviation or Term	Definition		
ABC-FX	aberrant behavior checklist (fragile X-specific factoring system)		
ADAMS	anxiety, depression, and mood scale		
AE	adverse event		
API	active pharmaceutical ingredient		
bid, BID	twice daily		
BMI	body mass index		
BP	blood pressure		
BPM	beats per minute		
CGI-I	clinical global impression improvement – investigator rated		
CGI-S	clinical global impression severity – investigator rated		
CNS	central nervous system		
СР	completer population		
CRF	case report form		
ECG	electrocardiogram		
ERP	event related potential		
FDA	food and drug administration		
FXS	fragile X syndrome		
IRB	institutional review board		
ITI	inter-trial interval		
ITT	intent to treat population		
KiTAP	test of attentional performance		
MEDRA	Medical Dictionary for Regulatory Activities		
mg	milligram		
n, N	number		
NIH-TCB	NIH toolbox cognitive battery for intellectual disabilities		
PI	principal investigator		
РК	pharmacokinetic		
РО	by mouth (per os)		
qd, QD	once daily (every 24 hours)		
SAE	serious adverse event		
SAP	statistical analysis plan		
SD	standard deviation		
SOC	system organ class		
SOP	standard operating procedure		

BPN14770 Clinical Study Report: I	3PN14770-CNS-203	Tetra Discovery Partners Inc.	
Statistical Analysis Plan Tetra Discovery Partners B	PN14770-CNS-203	Version 1.0 16 July 2020	
Abbreviation or Term	Definition		
VAS	visual analog scale		

Version 1.0 16 July 2020

2 STUDY OVERVIEW

This is a single center, Phase 2, randomized, double-blind, placebo-controlled, 2-period crossover study to obtain preliminary assessment of the effects of BPN14770 in subjects with Fragile X Syndrome. As schematic display of the study design is shown in Figure 1.

The study will consist of a Screening period of up to 28 days prior to initial study drug administration, followed by two 12-week double-blind treatment periods. The screening and the baseline visit for Period 1 may occur at the same time, provided the results of screening safety labs can be rapidly obtained. Subjects will be allowed to combine Period 1 Week 12 and Period 2 Day 1 visits. No washout period will be utilized between double-blind treatment periods; instead, efficacy and biomarker assessments during the second double-blind period (Period 2) will be obtained after a minimum of 6 weeks to allow for drug washout. A final follow-up phone contact for safety is planned one week after the conclusion of Period 2.

Eligible patients will be randomized in a blinded, balanced (1:1) fashion to receive either BPN14770 25 mg bid or matching placebo during Period 1, followed by the opposite treatment during Period 2.

Brief cognitive and behavioral assessments will be performed during each clinic visit. Safety and tolerability assessments throughout the study will include adverse event monitoring, ECGs, vital signs, blood chemistry, hematology, and urinalysis.

Pharmacokinetic samples will be collected at screening and at end of Periods 1 and 2 (Week 12) to confirm that study drug is present when expected and to estimate plasma exposure. Biomarker samples will be also collected at the time the pharmacokinetics samples are obtained.

[figure not shown]

Figure 1: Study Design Schematic

Study Duration

The total duration of the study of each subject will be up to 29 weeks, including a maximum of a 4-week screening period, two 12-week double-blind treatment periods, and a follow-up call approximately 1 week after last treatment.

Version 1.0 16 July 2020

Study Procedures

The Screening Visit will occur up to 28 days prior to the first study drug administration on Day 1. During screening, subjects and their parent/legal authorized guardian, if indicated, will review and sign an Informed Consent/Assent form prior to any study procedures being performed. Following confirmation of a prior diagnosis for Fragile X, subjects will have information collected regarding their neurological and medical/surgical history, race/ethnicity, social history (tobacco, alcohol, and/or drug use), and use of prescription and over-the-counter medications. Subjects will undergo a full physical exam, have vital signs measured, and 12-lead ECG performed. Height, weight, and BMI will also be collected. Fasting blood samples will be collected for chemistry and hematology, as well as biomarkers and pharmacokinetics. Urine will be collected for urinalysis. The Stanford-Binet test will also be administered at screening, as will an assessment of suicidality risk.

At the Baseline visit (Period 1, Day 1), prior to randomization, patients will receive an abbreviated physical examination including vital signs. However, these will not be repeated if the Screening and Baseline visits occur on the same day. Cognitive and behavioral evaluations will be performed, and these measurements will be used as a common set of baseline measurements to which post-treatment assessments will be compared for both treatment periods. During both double-blind periods, subjects will receive twice-daily treatment with blinded study medication as randomly assigned at baseline. Doses of study medication should be taken in the morning and at night, at least 6 hours apart and at least 30 minutes prior to or 1 hour after meals. Subjects will return to the clinic at the end of Weeks 2, 6, and 12 for each period. Cognitive and behavioral evaluations will be repeated at Weeks 6 and 12 for each period, with the exception of event-related potentials and eye tracking which will be repeated only at Week 12 for each period. Additionally, subjects will be monitored for adverse events, changes in concurrent medications and suicidality via a telephone call at the end of Week 1 of each period, and one week following completion of Period 2 (concurrent medications and AEs only). During clinic visits, adverse effects will be assessed, and laboratory measures, vital signs, and ECGs will be repeated per protocol. Suicidality risk with also be evaluated during the treatment periods per protocol; if a concern is detected, the subject will be referred for further evaluation and treatment. If a patient discontinues the study before Week 12 of a period, the clinical site will endeavor to collect all assessments to be completed at Week 12.

3 STUDY OBJECTIVES

3.1 Study Objectives

The objectives in this study are:

- To obtain preliminary assessment of the efficacy of BPN14770 25 mg bid,
- To evaluate the safety and tolerability of BPN14770 25 mg bid, and
- To obtain pharmacokinetic, pharmacodynamic, and biomarker data on BPN14770.

3.2 Exploratory Efficacy Endpoints

The following instruments will be used to assess the exploratory efficacy endpoints:

- NIH Toolbox Cognitive Battery Modified for Intellectual Disabilities (NIH-TCB)
- Test of Attentional Performance (KiTAP)
- Clinical Global Impression Severity Investigator rated (CGI-S)
- Clinical Global Impression Improvement Investigator rated (CGI-I)
- Visual Analog Scale (VAS) Rating Scale using patient-specific behavioral anchors
- Aberrant Behavior Checklist (ABC)
- Anxiety, Depression, and Mood Scale (ADAMS)
- Vineland-3 Rating Scale
- Event-Related Potentials (ERP)
- Eye Tracking

3.3 Safety and Tolerability Endpoints

The following safety assessments will be conducted during the study:

- Treatment-emergent adverse events
- Changes in vital signs
- Clinical laboratory evaluations (chemistry, hematology, urinalysis)
- Electrocardiogram (ECG) measurements

4 GENERAL METHODS

4.1 Analysis Populations

Safety Population: All subjects who sign the study-specific informed consent documents and receive at least one dose of study medication.

Intent to Treat (ITT) Population: All randomized subjects who receive at least one dose of treatment and return for at least one follow-up visit.

Version 1.0 16 July 2020

Completer Population (CP): All randomized subjects who complete both treatment periods with no significant protocol deviations.

4.2 Summarization of Data

Study results will be summarized by treatment group (Placebo or 25 mg BID) or treatment sequence (A-B, B-A), where appropriate.

No imputation of missing data will be performed. No windowing of visits will be performed unless otherwise specified.

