- Clinical Global Impression Improvement Investigator rated (CGI-I)
- Visual Analog Scale (VAS) rating using patient-specific behavioral anchors
- Aberrant Behavior Checklist (ABC)
- Anxiety, Depression, and Mood Scale (ADAMS)
- Vineland-3 Rating Scale
- Event-Related Potentials (ERP)
- Eye Tracking

Safety and Tolerability Endpoints

- Treatment-emergent Adverse events
- Changes in vital signs
- Clinical laboratory evaluations (chemistry, hematology, urinalysis)
- Electrocardiogram (ECG) measurements

Pharmacokinetic Evaluations

• BPN14770 plasma levels obtained at various time points during the study, according to the Schedule of Assessments

Study Design

This is a single-center, Phase 2, randomized, double-blind, placebo-controlled, 2-period crossover study to obtain preliminary assessment of the effects of BPN14770 in patients with Fragile X Syndrome. The study will consist of a Screening period of up to 28 days prior to initial study drug administration, followed by two 12-week double-blind treatment periods. The screening and baseline visits may occur at the same time, provided the results of safety labs can be obtained. No washout period will be utilized between double-blind treatment periods; instead, efficacy and biomarker assessments during the second double-blind period (Period 2) will be obtained no sooner than Week 6 of Period 2 to allow for drug washout. A final follow-up visit or phone contact for safety is planned one week after the conclusion of Period 2.

[figure not shown]
Eligible patients will be randomized in a blinded, balanced (1:1) fashion to receive either BPN14770 25mg bid or

Name of Sponsor/Company:	Tetra Discovery Partners, Inc.
Name of Investigational Product:	BPN14770
Study Title:	A Randomized, Double-blind, Placebo-controlled, 2-period Crossover Study of BPN14770 in Adult Males with Fragile X Syndrome
Study Number:	BPN14770-CNS-203
Study Phase:	Phase 2

matching placebo during Period 1, followed by the opposite treatment during Period 2.

Brief cognitive and behavioral assessments will be performed during each clinic visit. Safety and tolerability assessments throughout the study will include adverse event monitoring, ECGs, vital signs, blood chemistry, hematology, and urinalysis.

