6.4 Subject Withdrawal

All subjects have the right to withdraw from this study at any time. In addition, it is the right of the Investigator to remove subjects from the study as a result of adverse reactions, a protocol violation, or non-compliance, or any other reason. Subjects must be discontinued for the following reasons:

- Subject withdraws consent or requests discontinuation from the study for any reason;
- Occurrence of a medical condition or circumstance that exposes the subject to substantial risk and/or does not allow the subject to adhere to the requirements of the protocol as determined by the Investigator;

Protocol: BPN14770-CNS-203 Tetra Discovery Partners, Inc.

Date: 25 June 2018 Confidential

• Any serious adverse event (SAE), clinical significant adverse event, severe laboratory abnormality, concomitant illness, or other medical condition which indicates to the Investigator that continued participation is not in the best interest of the subject;

- Requirement for prohibited concomitant medication;
- Termination of the study by the Sponsor or the regulatory authority.

Should a subject withdraw after administration of BPN14770 (or placebo), or should the Investigator decide to withdraw the subject, all efforts will be made to complete and report the protocol-stipulated observations up to the time of withdrawal. Week 12 procedures (see Section 10.3.5 and Section 16.1 Schedule of Study Assessments) will be completed at the time of the subject's withdrawal and an explanation provided as to why the subject is withdrawing or being withdrawn from the study.

In a case of subjects lost to follow-up, attempts to contact the subject must be made and documented in the subject's medical records.

The Investigator must document the primary reason for discontinuation of a study subject on the appropriate case report form (CRF). If the reason for withdrawal is a clinical AE, monitoring will continue until the AE resolves or the Investigator assesses the AE as chronic and stabilized.

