10.3.7 Early Termination

It is hoped that all subjects can be followed through to the conclusion of the study at Period 2/Week 13. However, if an early termination occurs, the Week 12 procedures should be completed at the time of the subject's withdrawal (if possible) and an explanation provided as to why the subject is withdrawing or being withdrawn from the study. Procedures to be completed early termination:

- Collect weight;
- Collect vital signs;
- Conduct ECG (single);
- Draw fasting blood samples for Chemistry and Hematology (following a minimum 8-hour fast);
- Collect urine for safety urinalysis;
- Assess suicidality;
- Draw blood sample for pharmacokinetic analyses;
- Conduct the following cognitive tests:
 - o NIH Toolbox Cognitive Battery for Intellectual Disabilities (NIH-TCB)
 - o Test of Attentional Performance (KiTAP)
 - Clinical Global Impression Severity Investigator rated (CGI-S)
 - o Clinical Global Impression Improvement Investigator rated (CGI-I)
 - Visual Analog Scale (VAS) assessment of patient-specific behavioral anchors
 - Aberrant Behavior Checklist (ABC)
 - o Anxiety, Depression, and Mood Scale (ADAMS)
 - o Vineland-3 Rating Scale
 - Event-Related Potentials (ERP)
 - Eye Tracking

Protocol: BPN14770-CNS-203 Tetra Discovery Partners, Inc.
Date: 25 June 2018 Confidential

- Collect study medication and record pill count remaining in bottle to assess dosing compliance;
- Record any updates to concomitant medication use;
- Assess and record and adverse events; and
- Record final subject disposition.

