8 COGNITIVE TESTING ANALYSIS

8.1 NIH-Toolbox Cognition Battery (NIH-TCB)

The NIH-TCB is a battery of extensively validated computer-administered cognitive tests with utility across childhood and adolescence, early adulthood, and old age. The NIH-TCB assessments were designed to minimize floor and ceiling effects which often are present in testing batteries designed for the general population. Downward extensions of many of the NIH-TCB tests have been created to allow feasibility down to a mental age of 3. Therefore, there is good reason to believe that the assessments are appropriate for individuals with intellectual disabilities.

NIH-TCB includes the following evaluations/composite scores:

- Picture Vocabulary
- Oral Reading Recognition
- List Sorting Working Memory
- Pattern Comparison Processing Speed
- Picture Sequence Memory
- Flanker Inhibitory Control and Attention
- Dimensional Change Card Set
- Cognition Crystallized Composite Score
- Cognition Fluid Composite Score
- Cognition Total Composite Score

Summary statistics (n, mean, standard deviation, minimum, median, and maximum) will be presented for the observed values and the change-from-baseline values to each posttreatment time point for the uncorrected standard scores, the dext raw scores, and the dext raw percentages if available for each of the above evaluations/composite scores for the ITT population and the completer population. In these displays, baseline will be defined as the last non-missing value obtained prior to first dose of study medication for Period 1, Day 1 predose

The primary uncorrected standard scores are the uncorrected standard scores for cognition crystallized composite, picture vocabulary, oral reading recognition, pattern comparison processing speed, and picture sequence memory. The primary uncorrected standard scores will be analyzed using a mixed effect model. The change from baseline will be used in the model as the dependent variable. The model will include sequence, period, treatment, visit, predose baseline NIH-TCB, baseline Stanford-Binet Full IQ score, and visit by treatment interaction as

Version 1.0 16 July 2020

fixed effects, with subject within sequence as a random effect. This analysis will be done for both the ITT population and the completer population.

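### Do efficacy records collected at early termination, especially before Week 6 of Period 2, need an analysis rule in the SAP?

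*SAP*

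**What the plan says.** SAP section 2 replaces a washout with a delay: "efficacy and biomarker assessments during the second double-blind period (Period 2) will be obtained after a minimum of 6 weeks". The Protocol Synopsis (Study Design) words it as "efficacy and biomarker assessments during the second double-blind period (Period 2) will be obtained no sooner than Week 6 of Period 2", and Protocol 5.1 agrees.

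SAP section 2 also covers withdrawals: "If a patient discontinues the study before Week 12 of a period, the clinical site will endeavor to collect all assessments" due at Week 12. Protocol 10.3.7 says "if an early termination occurs, the Week 12 procedures should be completed at the time of" withdrawal, if possible. The footnote to the Protocol 16.1 schedule repeats this, and the schedule heads one column as both Period 2 Week 12 and early termination. Protocol 6.4 has the same instruction. None of these sets a minimum time in the period.

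On analysis, SAP 4.2 states "No imputation of missing data will be performed. No windowing of visits will be performed unless otherwise specified". The models in SAP 8.1 to 8.5 have a visit term without listing its levels; for the NIH-TCB, "The model will include sequence, period, treatment, visit, predose baseline NIH-TCB, baseline Stanford-Binet Full IQ score, and visit by treatment interaction". ABC, ADAMS, ERP and eye tracking (SAP 8.6 to 8.9) are modelled as change to Week 12. No section assigns a withdrawal record to an analysis visit.

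**The concern.** A subject who leaves at, say, Week 3 of Period 2 falls under both statements. Nothing is to be measured before about Week 6, yet the full battery is to be attempted on leaving. Such a subject can belong to the intent-to-treat population, which needs only one dose and one follow-up visit (SAP 4.1) and is the primary efficacy population (Protocol 11.3).

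The delay is the only stated protection against carry-over, and Protocol 4.2 reports that behavioural benefit in mice lasted two weeks after the drug was washed out. If a Week 3 record were analysed as Week 12, a subject given drug first could still show drug effect under placebo, and one given placebo first might not yet show the full effect of drug. Both pull the treatment contrast towards zero. If the SAP does not settle how to treat the record, the choice could be made with data in hand, in a study that reads unadjusted p-values below 0.05 as an indication of effect (SAP 4.4).

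**Working it through.** **Inputs from the documents.** SD 3 units, effect 2.25 units on the ABC, 30 crossover subjects, 15 per sequence, 5% alpha, 80% power (Protocol 11.1, SAP 4.3). A two-sided test is assumed.

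**Inputs that are assumptions.** The documents give no dropout rate or size of carry-over.
- k = subjects who leave before Week 6 of Period 2 and give a record, averaged as an even split between sequences. For k = 1 and 3 this is an expectation, since an odd number cannot be split evenly.
- c = share of the drug effect still present under placebo (drug-first subjects).
- s = share of the drug effect not yet reached (placebo-first subjects).

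**The plan's own figure.** Reading SD 3 as the within-subject SD, SE = 3 × √(2/30) = 0.775. Noncentral t with 28 df gives power 0.801 at 2.25 units, so the stated 80% is reproduced.

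**Records counted as Week 12.** Each sequence has k/2 affected subjects of 15. The mean contrast falls by the fraction c × k/30 in one sequence and s × k/30 in the other. Averaging the two sequences gives

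expected contrast = 2.25 × (1 − (c + s) × k/60), with SE still 0.775 and 28 df.

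**Records left out.** The contrast stays at 2.25 if leaving is unrelated to outcome. SE = 3 × √(2/(30 − k)), with 28 − k df.

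| k | Counted, c = 1, s = 0: contrast | Power | Left out: SE | Power | Power difference | Counted, c = s = 1: contrast | Power |
|---|---|---|---|---|---|---|---|
| 1 | 2.21 | 0.787 | 0.788 | 0.786 | 0.001 | 2.18 | 0.774 |
| 3 | 2.14 | 0.759 | 0.816 | 0.754 | 0.005 | 2.03 | 0.714 |
| 6 | 2.03 | 0.714 | 0.866 | 0.700 | 0.014 | 1.80 | 0.612 |

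With full carry-over alone the bias is k/60: 1.7%, 5% and 10%. At k = 6 that is 2.25 × 0.10 = 0.225 units, or 0.225/0.775 = 0.29 of a standard error. Counting the records gives slightly more power than dropping them. Dropping them wins on power only in the outer case, where carry-over is complete and none of the drug effect has yet appeared in the other sequence.

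**The passages side by side.** The 6-week statement stands in the design description and explains why the scheduled Period 2 battery starts at Week 6. The withdrawal passages deal with a subject who will have no later visit. SAP section 2, Protocol 10.3.7 and the 16.1 footnote qualify the collection as an endeavour or as done if possible. This is a rule and its usual exception. SAP section 2 also names Weeks 6 and 12 as the repeat efficacy visits, which points to two visit levels in the models of SAP 8.1 to 8.5.

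**The case for a change.** The strongest case is that the gap lies in the primary population and can matter after a single withdrawal. If early termination were entered as a third visit level, one such record would leave the treatment-by-visit design short by one rank (7 of 8), and a treatment difference averaged equally over visits could not be estimated. With one record per treatment its SE would be 1.66 to 1.71, against 0.56 to 0.57 with those records dropped (within-subject SD 3, between-subject SD 3 or 6 assumed, covariates omitted). The completer analysis checks the intent-to-treat result but does not define what that population contributes.

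The algebra is right. It needs two choices that the SAP does not state: a third visit level, which sits badly with the two named visits, and equal weighting over all levels. The Week 12 contrast has SE 0.79 whether the records are kept as a separate visit or dropped. An analyst who met a non-estimable contrast or a tripled standard error would see the cause at once.

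What stands is the silence itself. The schedule's shared column favours Week 12 for a Period 2 withdrawal, but it governs collection rather than analysis. The same silence covers Period 1 withdrawals and the Period 1 Week 12 ANCOVA, which the figures here do not address. Specifying the handling would be tidy, but either choice is acceptable, so the SAP states no rule that gives a wrong answer and no better method is being passed over.

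**Conclusion.** No change follows. The SAP leaves a detail open, and both sensible ways of filling it give nearly the same power. With full carry-over and 1 to 6 affected subjects, counting the records as Week 12 costs a bias towards zero of 1.7% to 10%, and power differs from leaving them out by 0.001 to 0.014. The wider loss, to a contrast of 1.80 and power 0.612, needs six such subjects with complete carry-over and no onset of effect. All of this rests on assumed numbers of withdrawals and assumed persistence, and on the protocol's ABC figures.

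Every crossover efficacy model is also run in completers (SAP section 8), a population that excludes anyone who does not finish both periods (SAP 4.1). Protocol 11.3 plans that population to test the robustness of the intent-to-treat results. It comes close to leaving the records out, because a subject with no usable Period 2 value adds little to a within-subject comparison. Period 2 withdrawals cannot touch the Period 1 ANCOVA. The study is declared exploratory (SAP 4.3, 4.4), and the direction of the bias would not create a false signal of benefit.
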